2. OBJECTIVES

2.1: Primary Aims

Note: This randomized clinical study should be considered a feasibility study to determine the ability to design and run a protocol of this nature. Each Aim was specifically selected

to maximize the possibility that novel information could be obtained from this trial. However, power calculations and associated precision estimates should be considered preliminary, as the data derived from this study will inform the calculations necessary to design a larger, more definitive study.

Aim 1:

To characterize the physiologic differences between ≥ 30 vs ≤ 10 day-old units. As part of the randomized study, we will measure PS exposure on donor red cells, as well as PE, microparticles, plasma free hemoglobin, heme, and NTBI. We hypothesize that ≥ 30 day-old units will have significantly more **biochemically old units** (see section 10 for the definition) than <10 day-old units. With a total sample size of 40 patients (20 in each group), we will have at least 80% power ($\alpha=0.05$) to detect a difference of at least 47% between the two randomized groups for biochemically old red cell units (close to a 100% difference is expected).

Aim 2:

To quantify whether physiologic differences between ≥ 30 day-old units versus ≤ 10 day-old units promote immune cell activation in transfused adults with SCD. We will perform flow cytometry to measure the activation of monocytes and neutrophils, as well as measure cell-free hemoglobin, heme and NTBI on blood samples before, 2, and 24 hours after transfusion. We hypothesize that those administered ≥ 30 day-old (biochemically old) units will have a greater increase in the number of CD62L + activated monocytes at 2 hours post-transfusion compared to those administered <10 day-old units. With a sample size of 40 patients, we will have 80% power ($\alpha=0.05$) to detect a change in MFI ratio of 1.35.

Aim 3:

To explore whether the physiology of ≥ 30 day-old units versus ≤ 10 day-old units is associated with adverse clinical outcomes in transfused adults with SCD. We will perform a systematic evaluation of hospital admissions, pain scores, medications, and clinical symptoms prior to each transfusion and at the end of the study period (**Table 1**). We hypothesize that reports of infection will be greater in subjects randomized to receive ≥ 30 day-old older units.

2.2 Secondary Aims

Aim 1:

To explore whether: ≥ 30 day-old units will have significantly greater mean 1) phosphatidylethanolamine expression, 2) cell free hemoglobin concentration, 3) cell free heme expression, and/or 4) NTBI expression in comparison to ≤ 10 day-old units.

Aim 2:

To explore whether:

- 1) Those administered ≥ 30 day-old units will have a greater increase in the number of activated monocytes or neutrophils as defined by flow cytometry markers of activation at 2 or 24 hours post-transfusion compared to those administered ≤ 10 day units.
- 2) Those administered ≥ 30 day-old day units will have a greater increase in the concentration of NTBI, cell free hemoglobin, and free heme, compared to those administered ≤ 10 day-old units at 2 or 24 hours post transfusion.
- 3) Recipient RBC PS, PE, and microparticle expression will increase more between 2 and 24 hours after receiving ≥ 30 day-old units than after receiving ≤ 10 day units.

Aim 3:

To explore whether those administered ≥ 30 day-old units will have a more rapid increase in the concentration of HbS% and a more rapid decrease in hemoglobin over time compared to those administered ≤ 10 day-old units.

Aim 4:

To explore whether those administered ≥ 30 day-old units will have a significantly different RBC metabolomic profile 2 and 24 hours post transfusion than those provided ≤ 10 day-old units.

Aim 5:

We will address aspects of study feasibility, such as subject drop-out, rates of missing data, and the confidence intervals/precision of our recorded variables, including PS, PE, microparticles, CD62L, and the other recorded clinical variables.

3. STUDY POPULATION

3.1 Enrollment Inclusion Criteria

- 1) Ages 16 to 60 years old
- 2) Subject must have sickle cell anemia confirmed by hemoglobin analysis
- 3) Must be receiving chronic red cell transfusion therapy
- 4) Must be outpatient at the time of transfusion

3.2 Enrollment Exclusion Criteria

- 1) History of severe reactions to transfusion therapy
- 2) Receiving red cell units that are crossmatch incompatible
- 3) Current participation in another therapeutic trial for SCD
- 4) Current pregnancy (due to the rapidly changing blood volumes that would alter the number of units needed for successful randomization, and due to the increased likelihood of hospitalization during the study protocol)
- 5) History of HIV infection

- 6) Having an uncontrolled inter-current illness, or psychiatric illness/social situations that would limit compliance with study requirements.

4. TRIAL ENROLLMENT

4.1 Screening/Recruitment

Patients ≥ 16 years of age undergoing outpatient red cell transfusion therapy will be identified through either the adult outpatient sickle cell clinic at UNC, the Infusion Clinic at UNC and at Emory/Grady Health System. Emory/Grady Health System will only enroll subjects who are ≥ 18 years of age. Basic features of patient medical and surgical histories (i.e. age, gender, reason for receiving chronic transfusion therapy) will be recorded.

Potentially eligible patients, as described in the previous paragraph, will be approached for study consent prior to their transfusion. Individual center scheduling practices will influence how this contact is arranged. Subjects who consent to the study will be assigned a study ID number and have their eligibility status evaluated. If the subject is eligible for the study based on the inclusion/exclusion criteria (section 3.1 and 3.2), they will be enrolled in the study and will be randomized. The availability of suitable products (see sections 4.2 and 5.1) will be determined when the study will start for that individual.

If a subject is enrolled and receives a red cell transfusion prior to randomization, that subject will still be randomized, and will start the study at their next outpatient red cell transfusion appointment, pending the availability of the appropriately aged units.

4.2 Stratification and Randomization

Subjects will be randomized to receive RBCs stored either ≤ 10 days at time of transfusion or ≥ 30 days at the time of transfusion. Storage arm assignment applies to up to 3 consecutive outpatient transfusions, beginning at the time of randomization and continuing through the end of the 3rd randomized outpatient transfusion. Randomization assignment can occur at any time between the date of consent till 2-3 days prior to the first study transfusion. Only the transfusion service will have access to the randomization assignment as designated by the study biostatistician.

Due to the pilot nature of this study, randomization will not be stratified by gender, age, ethnicity, or hemoglobinopathy type.

For the first study transfusion, after the number of units requested for crossmatch is known, but no earlier than 2-3 calendar days before transfusion, a study staff member will contact the institution's transfusion service to determine whether the transfusion service has enough suitable units stored ≤ 10 days and ≥ 30 days to meet the crossmatch request for this subject.

If there is not sufficient inventory to meet the randomization criteria, the subject's study participation will be postponed, and unit availability will be assessed again prior to their next outpatient transfusion.

Once the subject has received their first study transfusion, the remaining 2 outpatient study transfusion events will occur regardless of whether the transfusion service can meet the transfusion needs of the study.

4.3 Masking of Treatment Allocation

At enrollment, the subject's eligibility status and ABO/Rh type will be entered into the data management system. If eligible, the subject will be randomized at the time of consent, but no later than 2-3 calendar days before the first outpatient study transfusion. Unit age availability will be assessed no earlier than 2-3 calendar days before the first outpatient study transfusion, and the study will commence if unit availability is satisfactory for that subject. The study start will be delayed until the next outpatient transfusion if blood unit availability is deemed insufficient for that first study transfusion. Only blood bank staff with the appropriate security level in the data management system will be able to access the treatment arm assignment. Access to case report forms containing information about the age of the RBC products sent for each subject will also be restricted at the site to the appropriate blood bank staff. Clinical staff overseeing the subject's participation in the trial, collecting data, and reporting the data into the data management system will not have access to the treatment arm assignment or information about the age of the RBC products transfused.

No alteration will be made to the labels on the RBC units. The expiration date, collection date, and any processing dates (e.g. irradiation dates) will not be obscured. Medical infusion clinic personnel physically providing the RBC transfusions will verify product and patient identity according to hospital-specific procedures. These personnel will be instructed to not divulge the patients' randomization assignments. Other infusion clinic staff (other than those actually infusing RBCs), will be instructed not to seek to identify the age of the products the patients are receiving. The subjects themselves will not be informed of their randomization assignment and will also be instructed not to seek to identify the age of the products they are receiving. However, as the key components of this study are objective, inadvertent unblinding of the randomization assignment will not compromise the validity of the study.

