10.2. Analysis Plan

The analysis will be an intent to treat (ITT) with all those randomized being included in the study. For all aims, the distribution of, and relationship between, variables will be explored with summaries, plots, and tree analysis. All statistical estimates of population parameters will be tabulated along with corresponding confidence intervals (CIs). All hypothesis tests yielding large p-value (e.g., $p > \alpha$) will be reported as being inconclusive. [name], the lead biostatistician, or her designee, will perform these analyses. Where necessary for parametric assumptions, appropriate transformations will be employed with justification for their use; otherwise, non-parametric tests will be used. P-values will be reported without dichotomization wherever applicable. Data obtained from transfusion events where units of the appropriate age could not be obtained (study deviation) will be excluded from a subanalysis of the dataset, and the same distribution of, and relationship between, variables will be explored with similar summaries, plots, and tree analysis as in the ITT analysis. All subjects, regardless of age and gender, will be analyzed together as one cohort. Statistical software used in this study will be Cytel, StatXact and LogXact, SAS version 9.4, and Salford systems CART (Classification and Regression Trees). To adjust for multiple comparisons, we will use the false discovery rate approach which is less conservative than the Bonferroni approach. *Missing data:* Logistic regression will be used to investigate the possible causes for missing data and to investigate if data are missing at random (MAR). Reasons for missing data will be documented in the study database. We do not anticipate any missing data or drop-outs, but we will monitor these events. Assuming data are MAR, multiple imputations will be used for items, and for repeated measures, a random effects models will be used; the structure for the variance covariance matrix will be explored under the constraints of sample size. A sensitivity analysis will also be performed to evaluate the robustness/fragility of the study's main results to reasonable perturbations of the statistical methods and assumptions used. Results of the sensitivity analyses will only be used to guide trust in the main results.

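### Randomisation may precede the unit-stock check, so a randomised patient may never start yet stays in the ITT set without outcome data

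*Combined protocol and SAP*

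**What the plan says.** **When randomisation happens.** Section 4.3: "the subject will be randomized at the time of consent, but no later than 2-3 calendar days before the first outpatient study transfusion". Section 4.2 is wider: "Randomization assignment can occur at any time between the date of consent till 2-3 days prior to the first study transfusion". Section 4.1 has eligible subjects enrolled and randomised, and then adds: "The availability of suitable products (see sections 4.2 and 5.1) will be determined when the study will start for that individual".

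**When stock is checked.** Section 4.3: "Unit age availability will be assessed no earlier than 2-3 calendar days before the first outpatient study transfusion". Under section 4.2, study staff ask the transfusion service whether it has "enough suitable units stored ≤ 10 days and ≥ 30 days to meet the crossmatch request for this subject". The transfusion service is the party that holds the assignment.

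**If stock is short.** Section 4.2 opens the rule with "If there is not sufficient inventory to meet the randomization criteria". The start is then put off and stock is looked at again before the next outpatient transfusion. Neither section 4.2 nor section 4.3 limits the number of postponements.

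**When the assignment begins.** Section 4.2 has it "beginning at the time of randomization and continuing through the end of the 3rd randomized outpatient transfusion". Section 5.1 instead counts study units from the first study transfusion.

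**Who is analysed.** Section 10.2: "The analysis will be an intent to treat (ITT) with all those randomized being included in the study". The same section expects neither missing data nor drop-outs, and the Synopsis sets the goal as 40 randomised subjects.

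**The concern.** The stock check decides whether a patient starts, but it may come after assignment. A patient who fails it is randomised with nothing to analyse. Section 6.7 ends participation for withdrawal, loss to follow-up or no further need of outpatient transfusion, and does not require that a study transfusion took place. Such a patient has no study units for Aim 1, no 2-hour CD62L value for Aim 2 and no post-transfusion infection window for Aim 3.

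Section 10.2 offers only general tools: multiple imputation and random effects models assuming data missing at random. It does not say whether they apply to a patient who never entered the treatment phase. The analyst would have to impute the whole outcome, set it by convention, or drop the patient and depart from the stated ITT set. Because the target counts randomised subjects with no allowance, each non-starter also lowers the effective sample size.

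A smaller problem follows from the two starting points of the assignment. A postponed patient may be transfused with units of any age in the meantime. Under section 4.2 that transfusion falls inside the assigned period; under section 5.1 it is not a study transfusion.

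**Working it through.** **Sequence**

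1. Randomisation runs from consent to 2-3 days before the first study transfusion (4.2, 4.3).
2. The check falls no earlier than 2-3 days before that transfusion (4.2, 4.3). Randomisation therefore comes before the check or, at the latest, in the same window.
3. A failed check postpones the start to the next outpatient visit, without limit. Section 6.8 defines chronic transfusion as a 3-8 week schedule, so each failure typically costs that long.
4. Exit before any study transfusion is possible (6.7).
5. The patient remains in the ITT set (10.2).

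**Size for Aim 2**

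Inputs from sections 2.1 and 10.2.1: two-sided two-sample t-test on the log scale, alpha 0.05, at least 80% power for a ratio of 1.35. The total is 40, taken as 20 per arm. The SD is not given, so the 80% cannot be reproduced independently, but the SD it implies can be found:

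- Standardised difference giving exactly 80% power at 20 per arm: 0.909.
- ln(1.35) = 0.300, so the implied log-SD is 0.300 / 0.909 = 0.330.

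Holding that SD and the ratio of 1.35, with data from starters only:

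| Starters per arm | Power | Ratio detectable at 80% power |
|---|---|---|
| 20 | 80.0% | 1.35 |
| 19 | 77.8% | 1.36 |
| 18 | 75.5% | 1.37 |
| 16 | 70.1% | 1.40 |

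If non-starters are instead counted with no treatment effect among 20 per arm, the log difference shrinks to 0.300 × (1 − f), where f is their share. Power is then 71% at f = 10% and 61% at f = 20%.

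**Size for Aim 1**

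The plan claims at least 80% power for a 47-point difference with 20 per arm (Fisher exact test). Base rates and sidedness are not stated. A two-sided test gives 98.8% power if the lower rate is 0, 87.0% at 0.10, 79.5% at 0.20 and 77.3% at worst (26.5% vs 73.5%). The claim is thus roughly reproduced. Since the plan expects a difference close to 100%, Aim 1 can absorb some non-starters.

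**Numbers needed if the order stays**

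To obtain 40 starters, randomise 40 / (1 − f), rounded up. Assumed shares of 5%, 10% and 20% give 43, 45 and 50.

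**The case against.** **Randomisation at consent is only one permitted timing.** This is correct. Section 4.2 lets assignment wait until the check window, and section 4.1 foresees an enrolled patient being transfused before randomisation. But nothing makes the check come first, so the problem remains possible.

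**Postponed is not the same as never started.** Also correct: patients return regularly and stock is rechecked. The documents give no rate of non-starting.

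**The plan has tools for this.** Section 10.2 records reasons for missing data and provides for sensitivity analysis, and secondary Aim 5 makes drop-out and missing data feasibility outcomes. Non-starting would be measured, but its place in the primary analyses would still be undefined. Analysing only patients who were randomised and started would be simple, but would abandon the stated ITT set.

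**A reader might infer that the ≥30-day arm loses more patients because old units are scarcer at UNC.** The documents do not support this:

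- The check as worded in section 4.2 asks for both ages, so failure should not depend on arm.
- Section 1 (Preliminary Studies) gives a UNC mean of 18 days, SD 10, range 5-39. A plain normal curve puts 21.2% of units at ≤10 days and 11.5% at ≥30, but it also puts 9.7% below the observed minimum. Restricted to 5-39 days, the shares are 13.0% and 11.0%.
- These are ages of transfused units, not of stock. The retrospective series in the same section has 32% at ≥30 days.

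What stands is narrower. The references to the randomisation criteria (4.2) and to availability being adequate for the individual subject (4.3) could be read as meaning the assigned arm only, and the service that answers knows the arm.

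**Conclusion.** The concern holds as a sequencing flaw that should be corrected. Followed as written, the plan can produce randomised patients with no outcome data, whom section 10.2 includes and does not provide for. The expected harm is mainly arm-neutral loss of data and power. Arm-differential loss is a conditional risk that depends on how the check is read in practice.

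One to four non-starters per arm would lower Aim 2 power from 80% to between 77.8% and 70.1%. This assumes equal losses, data from starters only and the back-solved log-SD of 0.330; the number of non-starters is illustrative. The loss is modest, in a study that section 2.1 calls a feasibility study with preliminary power figures, but it is avoidable.

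**What to change.** For subjects not yet randomised, state one order in sections 4.1-4.3:

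1. Consent and eligibility.
2. Within the existing 2-3 day window, a recorded confirmation that enough suitable units of both ages are in stock.
3. Release of the next allocation.

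Patients whose check fails stay enrolled but unrandomised until the next visit. The confirmation should be recorded before release because the Synopsis has the statistician give the schema to the blood bank.

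Reword the insufficiency rule in 4.2 and the matching sentence in 4.3 so that both plainly refer to the two-age check. Reconcile the start of the assignment period in 4.2 with the definition of study units in 5.1. Report by arm any patients already randomised who never started.

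The cost is mostly wording, since the check and its window already exist. The drawbacks are that allocation and unit selection fall in the same 2-3 days, and that subjects already randomised (the Synopsis mentions 15 enrolled at a previous site) will not have followed the new order.

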5. INTERVENTIONS

5.1 Preparation

In Section 5 of this protocol, the term "study RBC units" includes all RBC units provided to a randomized subject, beginning at the time of the first study transfusion and continuing through the end of study. Transfusions will always be ordered based on patient need, following all institutional policies and practices. The decision to order (or not order) an RBC transfusion is not dictated in any way by the study protocol

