Changes occur in the physiology of red cell units with prolonged storage that may trigger a cascade of deleterious events in the transfusion recipient: macrophage activation, inflammation and release of toxic iron species (Figure 1). Red cells preserved with Adsol solution can be stored up to 42 days,⁶⁵ a recommendation based on integrity, not red cell efficacy or safety. Significant oxidative and metabolic changes occur with storage: hemolysis with release of cell-free hemoglobin, heme, and non-transferrin bound iron (NTBI), as well as alterations to the lipid composition of the red cell membrane.⁶⁻¹⁵ Surface exposure of phosphatidylserine (PS), a phospholipid normally found on the inner leaflet of the red cell membrane but which becomes externally exposed with storage, may be the most important of these changes.²³⁻²⁷ Macrophages recognize PS as an “eat me” signal via specific receptors (Tim1, Tim4, and Stabilin-2) and rapidly phagocytize these red cells.⁶⁶⁻⁷¹ In pre-clinical studies, phagocytosis of old red cells results in activation and secretion of pro-inflammatory cytokines, such as IL-1, IL-6, IL-8, CXCL-1 and monocyte chemoattractant protein-1 (MCP-1).^{19,28} Phagocytosis of a bolus of old red cells also overwhelm the macrophage’s metabolic capacity, leading them to release cell-free hemoglobin, heme and NTBI with downstream effects.^{21,22,29-31} NTBI has been associated with fatal proliferation of ferrophilic bacteria and the generation of toxic reactive oxygen species.^{19-22,37-39} Of note, these effects on macrophages are only seen after the transfusion of older intact red cells, not from the products of lysed red cells, which suggests that phagocytosis of red cells is required to generate this pathophysiology.²⁹

Although some patients may be able to tolerate the aberrant physiology of older red cells, others may be at risk of poor outcomes.

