In Milwaukee, 1/3 of units transfused to adults with SCD are >30 days old, but nation-wide some restrict the transfusion of older units. Four hundred adults receive care in the Adult Sickle Cell Clinic at UNC in Chapel Hill, 47 of who receive chronic outpatient transfusions for chronic pain or stroke prophylaxis. Transfusions are administered to adults regardless of storage age. In a 3-year retrospective review of transfusions administered to adults with SCD, 896 units were transfused over 407 simple transfusion encounters. Median storage age was 23 days (range: 2-42 days); 32% of units provided were \geq 30 days-old (**Karafin et al., 2015**).⁴¹ To evaluate the opinions and policies of other hospital blood bank directors about the use of older red cell units for patients with SCD, we conducted a nation-wide survey (n=90). While only 23% of respondents had a storage age restriction policy for patients with SCD, 31% thought that older units were not as effective as younger units, and 65% believed that evidence-based policies were needed (**Karafin et al., 2015**).⁴⁰ These data from our institution and across the US demonstrate equipoise among blood bank directors about the potential harm of older units for patients with SCD. At UNC, we have determined that the average unit age transfused is 18 days, with a standard deviation of 10 days (range: 5 days- 39 days).

Transfusion of older units to adults with SCD stimulates expansion and activation of macrophages. Adults with SCD may be susceptible to the effects of an older unit's physiology because they are prone to infection, chronically inflamed, and poorly equipped to handle excess iron. In a cohort of 40 steady-state adults with SCD, we specifically measured markers of inflammation and iron excess. High sensitivity C-reactive protein, a marker of global inflammation, was found to be markedly elevated (median 5.6 mg/L, range 0.4-60 mg/L; reference range <1.0 mg/L), as was ferritin, a marker of iron stores (median 2,969 ng/ml, range 20-12,300 ng/ml; reference range 13-400 ng/ml) (**Karafin et al., 2015**).⁹³

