5.2 Administration

RBC units will be administered according to local institutional policy and safety standards as ordered by the medical team for patient care needs.

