6.5 RBC Transfusions

The following data will be collected for each RBC unit ordered for the subject while on study:

- Unit ID number
- Source of unit (apheresis or whole blood collection)
- Blood group of unit (ABO and Rh)
- Leukoreduction status
- Irradiation status
- Volume reduction/washed unit status
- Storage medium (AS1, AS3, or AS5)
- Antigens matched (D, Cc, Ee, Kk, or other)
- Collection or expiration date (specifically recorded by the blood bank to maintain study coordinator blinding)
- Start time and end time of transfusion

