The primary outcome measure is the change in CD62L (activated) circulating monocyte/macrophage MFI at 2 hours post-transfusion compared to the subject pre-transfusion. We will compare the two groups (\geq 30 day-old compared to \leq 10 day-old unit exposure) using a two sample two-sided t-test of the log at an alpha of 0.05. Power: We will have at least 80% power to detect a change in the ratio of 1.35 post-transfusion if the variability is similar to that seen in our preliminary data.

Exploratory: We will use a general(ized) linear model to include biochemically old units transfused (Aim 1 outcome), regardless of unit age, as a covariate in our analysis. Other co-variates in this model will include free heme, cell free hemoglobin, and NTBI. We will similarly compare other obtained activation measures as outcomes: activation markers for monocytes, neutrophils (as listed in section 6) and measured plasma cytokine

concentrations (section 6). We will also plan for auxiliary analyses of the outcome variables in which the explanatory variable is the age (days) of the RBC units --to characterize the degree to which age (days) can accurately predict the clinical and physiologic outcome measures defined. Lastly, as an exploratory aim, we will evaluate the *in vivo* change in recipient red cell PE/PS positivity at 2 and 24 hours post transfusion.

Aim 3:

The primary outcome variable is the rate of post-transfusion infections in the patient. The primary estimand is the treatment effect defined as the difference between the regimen-specific proportions of patients in the target populations that would experience post-transfusion infections. This population parameter will be estimated as a function of the proportions observed in the sample of patients studied. The point estimate will be reported along with the corresponding 95% confidence interval estimate. The presence of an indwelling catheter will be used as a key co-variate in this analysis. *Power:* A difference of 20% will be of clinical interest. We do not expect to have adequate power for this pilot study but at an alpha of 0.05 with 20 subjects in each group we will be able to detect a difference of 47% between the proportions.

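### The Aim 2 primary test leaves out the amount of blood ordered, although the protocol's own mechanism suggests that amount is prognostic; adjusting for the first-event unit request would gain precision at almost no cost

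*Combined protocol and SAP*

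**What the plan says.** - **Amount.** Section 5.1: "Transfusions will always be ordered based on patient need, following all institutional policies and practices". Section 5.2 has units given "as ordered by the medical team for patient care needs". No number of units or volume is set, and Section 4.2 does not stratify on either.
- **Procedure.** Section 3.1 requires chronic transfusion, which Section 6.8 defines only by an interval of 3 to 8 weeks. Neither mentions simple or exchange. The word simple is used only for the retrospective data in Section 1: "896 units were transfused over 407 simple transfusion encounters".
- **Mechanism.** Section 1: "Phagocytosis of a bolus of old red cells also overwhelm the macrophage", after which the cells release hemoglobin, heme and NTBI.
- **Record.** Section 6.5 collects data for each unit, from the unit number to "Start time and end time of transfusion". Units can be counted, but transfused volume and procedure type are not listed.
- **Analysis.** Section 10.2.1 compares the 2-hour CD62L change between arms "using a two sample two-sided t-test of the log at an alpha of 0.05", with no covariate. An exploratory model adds biochemically old units transfused, with heme, hemoglobin and NTBI.
- **Timing of the request.** For the first study transfusion, Section 4.2 has inventory checked "after the number of units requested for crossmatch is known", before units are released. The number is put to no other use.

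**The concern.** The arms differ in the age of the cells, but the mechanism concerns how many old cells arrive at once. If amount also drives the 2-hour CD62L change, patients given few units and patients given many will respond differently within each arm. An unadjusted test leaves that spread in the error term.

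Three things are at stake:

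- **Precision.** About 20 patients per arm leave little to spare.
- **Interpretation.** A reader of the result will ask whether the arms received similar amounts by similar procedures. The listed data answer this only in part.
- **Planning.** Section 2.1 says the data will inform the design of a larger trial. An SD that mixes unrecorded procedures is a weak input for that.

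The protocol already treats the number of units as relevant: Section 3.2 excludes pregnancy partly because changing blood volumes would alter the units needed.

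**Working it through.** **Inputs from the documents.** 20 patients per arm, two-sided alpha 0.05, at least 80% power, MFI ratio 1.35 (Sections 2.1 and 10.2.1); 896 units over 407 simple encounters (Section 1). The SD of the log change is not given, nor is the spread of units per transfusion or the share of patients on exchange.

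**1. The plan's own power.** It cannot be reproduced without the SD, so I solved for the SD it implies.

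- ln(1.35) = 0.300.
- With 20 per arm, a two-sample t-test has 80% power at a standardized difference of 0.909 (noncentral t, 38 df).
- Implied SD = 0.300 / 0.909 = 0.330. The normal approximation gives 0.339.
- Standard error of the arm difference = 0.330 × √(2/20) = 0.104.

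The 80% is attainable but cannot be verified.

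**2. Typical amount.** 896 / 407 = 2.20 units per simple encounter.

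**3. Gain from adjustment, if the SD of 0.330 already includes variation in amount.** Let R² be the share of within-arm variance that amount and procedure explain (assumed). Residual SD = 0.330 × √(1 − R²); detectable ratio at 80% power = exp(0.909 × residual SD).

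| Assumed R² | Residual SD | Power for 1.35 | Detectable ratio |
|---|---|---|---|
| 0 | 0.330 | 79.9% | 1.35 |
| 10% | 0.313 | 84% | 1.33 |
| 20% | 0.295 | 88% | 1.31 |
| 30% | 0.276 | 92% | 1.29 |

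Power allows for one covariate (37 df). With two covariates (36 df) and R² = 0 it is also 79.9% when rounded, so the loss is about 0.1 percentage point.

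**4. The other case: the SD of 0.330 excludes that variation.** The total SD is then 0.330 / √(1 − R²) = 0.348, 0.369 or 0.395 for R² of 10%, 20% or 30%, and the unadjusted test has 76%, 71% or 65% power. Adjustment would bring it back to about 80%. The documents do not show which case applies.

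**5. Chance imbalance, if exchange patients enrol (assumed share).** With 8, 12 or 16 such patients among 40 split 20/20, the hypergeometric probability that the arms differ by 4 or more is 24%, 30% or 33%. To size a 4-patient difference, attribute all of R² to procedure: effect of procedure = √R² × 0.330 / √(f(1 − f)), where f is the share on exchange; shift in the arm difference = that effect × 4/20.

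- f = 0.4, R² = 10%: 0.316 × 0.330 / 0.490 = 0.213; × 0.2 = 0.043; exp = 1.04; 0.043 / 0.104 = 0.4 standard errors.
- f = 0.2, R² = 30%: 0.548 × 0.330 / 0.400 = 0.452; × 0.2 = 0.090; exp = 1.09; 0.090 / 0.104 = 0.9 standard errors.

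**6. Type I error.** With equal mean response in both arms, and 25% or 50% of patients at three times the amount, 20,000 simulated trials each gave 5.2% and 5.1%.

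**The case against.** The best case for the plan is that testing storage age under usual ordering is a legitimate pragmatic choice. Section 2.1 calls the trial a feasibility study with preliminary power. Randomization deals with amount on average, and the t-test's standard error already allows for chance imbalance. All of this stands, so adjustment is a matter of efficiency and clarity, not a correction of an invalid test.

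Three further objections stand at least in part:

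- **Exchange.** A reader might infer from the eligibility wording that simple and exchange patients are mixed. The documents only leave it open, so the imbalance figures are conditional on an assumption.
- **Recoverability.** A reader might infer that an imbalance could never be recognized. Units can be counted from the per-unit record, Section 5.1.1 bars volume-reduced units, and procedure type should be obtainable from blood bank or clinic records.
- **CD62L.** The bolus sentence concerns release of hemoglobin, heme and NTBI. Extending it to CD62L is a reasonable inference, not a statement in the protocol.

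The exploratory model is a weaker answer. Its covariate, biochemically old units, is expected to differ by close to 100% between the arms (Section 10.2.1, Aim 1), so it nearly duplicates the arm and cannot stand in for the amount ordered.

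There is also a sound warning about the remedy. Secondary Aim 3 (Section 2.2) expects a faster fall in hemoglobin after older units. Requests at transfusions 2 and 3 could therefore depend on arm even if the ordering clinician is masked, and adjusting for them could remove part of the treatment effect.

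**Conclusion.** The point holds as a loss of precision and a risk to interpretation. Amount follows local ordering, the protocol's reasoning makes it plausibly prognostic, and the primary Aim 2 test does not use it. The size rests on an assumed share of variance: if the implied SD of about 0.33 already includes amount, power for a ratio of 1.35 goes from 80% to about 84%, 88% or 92% at 10%, 20% or 30% explained.

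Three stronger readings are not supported:

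- **Bias or inflated type I error.** The arms are randomized, and the simulated error stays near 5%.
- **A storage effect produced by imbalance alone.** Under the assumptions above, a 4-patient difference in procedure type moves the ratio by a factor of 1.04 to 1.09, well short of 1.35.
- **A wrong power statement.** The stated 80% cannot be checked without the SD, but nothing shows it to be wrong.

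**What to change.** 1. **Section 6.5:** add transfused volume and procedure type (simple or exchange) for each study transfusion. For the 15 subjects already enrolled, seek both from blood bank or clinic records.
2. **Section 10.2.1, Aim 2:** make the primary analysis a linear model of log CD62L change on arm, adjusted for the number of units requested at the first study transfusion that goes ahead. If both procedure types enrol, add the patient's type at that first event. Keep the unadjusted t-test as a sensitivity analysis.
3. **State why only the first request is used.** Section 4.2 allows randomization as early as consent, so the request may follow randomization. It still precedes release and any study blood, and Section 4.3 withholds the arm from clinical staff. Do not adjust for requests at transfusions 2 and 3.
4. **Arm-by-units term:** descriptive only, since no power for it has been shown.
5. **Report the SD of the log change** behind the power statement, and say whether it includes usual variation in amount.

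The ordering of transfusions stays as it is. The cost is two CRF fields, some SAP wording and one or two degrees of freedom.
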